Health
Sydney
Local Health District

PMBC Sleep Program

PROTOCOL NUMBER: VERSION 1.0 (APRIL 2018)

ADMINISTRATIVE INFORMATION

DATA CATEGORY	INFORMATION
Scientific Title	A pilot evaluation of sleep program to improve sleep quality in male psychiatric HDU inpatients
Public Title	PMBC sleep program
Date of Registration	TBC
Primary registry and trial identification number	TBC
Date of Registration in primary registry	TBC
Secondary identification numbers	TBC
Source of monetary or material support	Fully funded by the Sydney Local Health District (\$50,000)
Primary Sponsor	Sydney Local Health District
Contact for public queries	[name] [name], [contact]
Contact for scientific queries	[name] [name], [contact]
Countries of recruitment	Australia
Health condition(s) or problem(s) studied	Inpatient male HDU psychiatric patients of all diagnoses
Intervention(s)	Ward-based initiatives and activity groups
Comparator	Routine male inpatient psychiatric HDU patients' length of stay with and without therapy; previous admissions
Inclusion criteria	Males aged 18+ years. Able to give informed written consent. Literacy in English. Inpatient at PMBC psychiatric Male High Dependency Unit (HDU).
Exclusion criteria	Current substance dependence. Severely unwell such that not able to give consent or tolerating participation in group sessions. Severe cognitive impairment or thought disorder. Not

	proficient in English. Recent transmeridian (>2 time zones) travel (within last 1 month).
Study type	Interventional; Allocation: nonrandomized; Masking: none (open label trial)
Primary Purpose	Pilot Study, Feasibility Study
Date of first enrolment	May 2018
Target sample size	N/A (Pilot study, rolling recruitment)
Recruitment status	Recruitment not yet commenced.
Primary outcomes	Actigraphic changes in sleep duration (Respironics Actigraphy data)
Key secondary outcomes	
Sleep quality (weekly Visual Analogue Scale (VAS) and Pittsburgh Sleep Quality Index measured at start and end of study)
 
Self-report duration
 
Length of stay in HDU
 
Use of as needed (PRN) sedatives for sleep
 
Sleep efficiency (actigraphy)
 
Engagement in group
 
Autonomy
 
Participant satisfaction

Protocol Version:	Version 1.0, April 2018
Revision Chronology	Version 1.0, April 2018: Original.
Protocol Amendment Number	0
Authors	[name] BE(Hons) BCom MBBS, [name] BPsych(Hons), [name] MBBS PhD

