Polysomnography (PSG) is the gold standard technology for assessing sleep. It is objective, but it is also expensive and limited to just a few nights of data collection in a lab setting which would impede its ability to document sleep problems in a inpatient psychiatric ward. The polysomnography testing process can also interfere with sleep, especially on the first night. Benefits of actigraphy over traditional polysomnography is that you can record continuously for 24 hours per day for days, weeks or longer. Conversely, patient-reported sleep questionnaires are low cost, can be used for multiple nights, and likely do not interfere with sleep. However, they are imprecise and subjective. The subjective nature of questionnaires can be useful if the subjective sleep assessment is the therapy target but can be a problem if you want to detect changes in small Phase 2 or pilot studies. Monk et al. compared both actigraphs and sleep diaries to PSG during space flight. Predicted values of actigraphy were clearly superior to those of diaries for sleep onset and offset, sleep duration, and sleep efficiency.

Actigraphy has been used to investigate movement and sleep disturbance in psychiatric patients. Dursun et al. conducted a descriptive study of wrist actigraphy estimation of sleep in outpatients with schizophrenia prescribed risperidone compared to those on “typical” antipsychotics, and to normal controls. They found a greater degree of nighttime wrist movement (i.e., higher movement index) in patients on a typical antipsychotic compared to those on risperidone. Lemke et al. used wrist actigraphy to estimate mean activity levels in psychiatric unit inpatients with major depressive disorder (evidence level 4C-b).¹⁵³ They found that subjects whose Pittsburgh Sleep Quality Index indicated poor sleep had higher mean nighttime motor activity levels than those who reported good sleep. In addition, subjects with fewer depressive symptoms had lower mean nighttime motor activity levels than those with greater depressive symptomatology.

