In conclusion, scientific research suggests that in the clinical setting, actigraphy is reliable for evaluating sleep patterns in patients with insomnia, for studying the effect of treatments designed to improve sleep, in the diagnosis of circadian rhythm disorders (including shift work), and in evaluating sleep in individuals who are less likely to tolerate PSG, such as inpatient psychiatric patients. While actigraphy has been used in research studies for many years, it is only recently that the methodological issues have been systematically addressed in clinical research and practice. With those issues addressed, the use of actigraphy is now being applied to clinical practice. (Ancoli-Israel et al, 2003).

STUDY OBJECTIVES

Primary Objective

To evaluate the effect of the Sleep Program on duration of admission in HDU (compared to controls) and sleep duration (Actigraphy data), in male psychiatric HDU inpatient participants.

Secondary objectives

1. Sleep quality - improvement in the Pittsburgh Sleep Quality Index
2. Sleep efficiency- percentage time in bed vs percentage time asleep
3. To test the engagement (tolerability and practicality) with a structured Stimulus Control Therapy Program
4. Impact on use of as needed (PRN) hypnotics
5. To describe the characteristic of sleep, activity and light exposure of patients in a high dependency psychiatric unit using wrist actigraphy.

Hypotheses

- We hypothesise that a structured stimulus control program for sleep will shorten duration of admission at psychiatric HDU.
- There will be an improvement in the sleep duration and efficiency
- There will be an improvement in the quality of sleep via a reduction of the self-rated Pittsburgh Sleep Quality Index score, measured at the beginning and end of the study.
- Participants in the Bright Light Study will engage in a structured stimulus control therapy program and it will be well-tolerated.

STUDY DESIGN

Design, Study Groups, Number of Participants

This is a pilot study for a complex intervention and we do not know the effect of variance. We seek to test our methodology, exterminate recruitment and retention rates, feasibility and finally, determine the sample size. We also seek to highlight any issues with acceptability, compliance, and delivery of our interventions.

Number of centres

Single-centre, at [name] Centre, male High Dependency (psychiatric) Unit

Duration

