	Ward environmental initiatives
Stimulus Control Therapy	
 • Consistent wake time at 7am encouraged by ward staff • Beanbags: an alternate place to sit other than the bed
Sleep Psycho-education	
 • Visual cues regarding specific sleep hygiene strategies around patient room and ward area. • Reinforcement, encouragement and further psychoeducation provided by nursing staff
Increased light exposure (regulating circadian rhythm)	
 • Using available open spaces wherever possible enhanced with early morning Retimer™ blue-green light goggles for those with sleep-phase delay
Relaxation	
 • Calming music during wind down • Quiet space with dim lights and beanbags

Activity Groups

Each participant will be invited to participate in thrice-per-week, 30-minute workshops in the program, which aim to provide psychoeducation about sleep, debriefing and sleep-promotion related

activities. It is also aimed at increasing daytime activity and enforcing a regular circadian rhythm. This is conducted on a repeated weekly cycle as outlined below. These sessions will take place on the outdoor area of the HDU (the balcony) where possible such that participants will receive continuous daylight exposure during these sessions. Each session will take place in mid-morning to lunchtime.

Session 1

Session 1 are on Mondays. They are facilitated by a senior Occupational Therapist and a peer-support worker and is designed to instil a routine of activity (via a Cooking group). Initial consenting and program information will be provided to a patient who is commencing. As well, actigraph watch and sleep diary will be provided to the commencing participant, allowing for ongoing record and feedback of their sleep parameters throughout their time in the program. Qualitative feedback regarding sleep will be collected during these sessions.

Session 2

Second sessions are held on Wednesdays, on the balcony of the HDU. They are facilitated by two psychiatry registrars. Prior to the sessions, participants' actigraph watches are collected and sleep data analysed by the research assistant. A visual representation of sleep duration and activity for each patient will be printed prior to the session and given to the registrars, and printouts are identifiable only by participant IDs.

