These sessions are held as a mini picnic with healthy snacks. During these sessions, printouts will be discussed individually with participants, especially with respect to their self-evaluation in their Sleep Diaries. This aims to increase insight and empower the participants to take a proactive role in their management.

As a group, the registrars will give further psychoeducation about sleep, with a focus on sleep hygiene, and addressing specific stimuli which affect sleep.

Wednesday sessions are also repeated in a weekly cycle. Patients in their initial and final weeks of the program will be asked to complete the Pittsburgh Sleep Quality Index, modified to reflect the quality of sleep within one week.

Session 3

Session three are held on Fridays and are repeated on a weekly basis. It is split into two components. Firstly, the morning session is in the form of a breakfast barbeque – which is open to the entire ward to participate. Facilitators of sessions 1 and 2 are able to join. This session is an informal way for participants and clinicians to freely exchange ideas and feedback, as well as to reinforce sleep psychoeducation provided in earlier sessions.

Secondly, there will be a booster session on Friday evenings, which is self-directed by the participants and is optional. It entails participants making use of the ward measures made available to them – to enhance relaxation and stimulus control.

Summary table of sessions

Session	Day and time	Content	Measurement tools	
			Sleep diary	Actigraphy
1	Monday 11:30am – 12pm	
 • Cooking group • Preliminary psychoeducation • Program information and obtaining consent • Providing actigraph watch and diary for participant 	X	X
	Tuesday	Nil active intervention for Day 2 participants complete diary +/- nurse Day8 participants - maintain stimulus control and am light goggles	X	X
2	Wednesday (Pre- session)	
 • Collecting watches + analysing actigraphy 	X	X
	Wednesday 11:30am – 12pm	
 • Outdoor session with snacks • Psychoeducation about • Stimulus Control Therapy, Sleep Hygiene • Present sleep results • Administer PSQI and one-item Sleep Quality measure (start and terminating session only) 		
	Thursday		X	X
3	Friday AM	
 • Outdoors session with bacon and eggs 	X	X

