	Friday PM 9 - 9:30pm	
 • Booster session • Wind down with beanbags • Headphones provided for relaxing music • Reinforcing stimulus control therapy 	X	X

Participant Time Line

Time Frame for Activity	Screen	Program cycle		
		At recruitment	Weekly	At discharge
Initial screening in handovers by clinical staff	X			
Initial medical assessment for appropriateness	X			
Self-report measures		X	x	X
Sleep Diary			X	
Qualitative evaluation Questionnaire				X
Ward initiatives		X	X	
Retimer™ Light goggles			X	
Actigraphy data		X	X	
Sleep Program groups		x	X	
Psychoeducation about sleep hygiene		X	X	
Program usage		X	X	X
Adverse event monitoring		X	X	X

Study Procedure Risks

1. Skin damage due to photosensitivity
Some medications, notably Chlorpromazine, are known to increase the photosensitivity of the skin. The Program entails exposure to natural and low intensity artificial light, which may cause irritation and minor sunburns.
2. Headache from tightness or poor fit of light spectacles
The Retimer™ light goggle is made from rigid plastic and are not adjustable for size of head. Therefore, it is possible that participants may experience discomfort on the ridge of their nose, or sections of the skin around the auricle which makes contact with the goggle.
3. Discomfort from artificial light
The Retimer light goggle emits light in two different intensity settings, which is projected upwards towards the light. Whilst the light intensity is safe, it may still be a source of discomfort and annoyance to the patient.
4. Sleep disturbance
The Program is an evidence-based intervention aimed to reset and align the circadian rhythm to normal daylight hours. However, there is a risk that the integrated intervention does not improve sleep quality and quantity, or indeed, may worsen them.
5. Psychological harm: wearing a watch which constantly collects data might further enhance persecutory or paranoid ideations in the sub-population of participants who are experiencing psychotic symptoms. However, given the study requires informed consent, the likelihood of a paranoid patient consenting to participate is small.

Given the non-invasive, interactive and patient-driven nature of the intervention, it is expected that participants will have minimal risks in the following domains:

- disclosure of sensitive personal information
- exposure of illegal activity
- economic harm
- discrimination, stigma or other social harm
- devaluation or harassment

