Tryon, W. (2005). The reliability and validity of two ambulatory monitoring actigraphs. *Behavior research methods*, 37, 492-497

APPENDICES

Modified Pittsburgh Sleep Index

Sydney Local Health District

MODIFIED PITTSBURGH SLEEP QUALITY INDEX (PSQI)

ID NUMBER: _____

Instructions: The following questions relate to your usual sleep habits during the Past week only.

During the past week,

1. When have you usually gone to bed? _____
2. How long (in minutes) has it taken you to fall asleep each night? _____
3. When have you usually gotten up in the morning? _____
4. How many hours of actual sleep do you get at night? _____

5. During the past week, how often have you had trouble sleeping because you...	Not during the past week (0)	Less than once a week (1)	Once or twice a week (2)	Three or more times a week (3)
a. Cannot get to sleep within 30 minutes				
b. Wake up in the middle of the night or early morning				
c. Have to get up to use the bathroom				
d. Cannot breathe comfortably				
e. Cough or snore loudly				
f. Feel too cold				
g. Feel too hot				
h. Have bad dreams				
i. Have pain				
j. Other reason(s), please describe, including how often you have had trouble sleeping because of this reason(s):				
6. During the past week , how often have you taken medicine (or asked a nurse for tablet) to help you sleep?				
7. During the past week, how often have you had trouble staying awake while eating meals, or engaging in social activity?				
8. During the past week, how much of a problem has it been for you to keep up enthusiasm to get things done?				
	Very good (0)	Fairly good (1)	Fairly bad (2)	Very bad (3)
9. During the past week, how would you rate your sleep quality overall?				

[figure not shown]
Sleep Diary

[figure not shown]
	LAST NIGHT I WENT TO BED AT	LAST NIGHT I FELL ASLEEP AT	OVERNIGHT MY SLEEP WAS DISTURBED BY	THIS MORNING I WOKE UP AT	THIS MORNING I GOT OUT OF BED AT	MY SLEEP QUALITY WAS	DID YOU HAVE A NAP DURING THE DAY	HOW LONG
DAY 1						 Very Good  Good  Average  Bad  Very Bad	 Yes  Nohours minutes
DAY 2						 Very Good  Good  Average  Bad  Very Bad	 Yes  Nohours minutes

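### The five-row sleep diary and Monday-to-Friday measurement table leave at least two of seven nights, Saturday among them, without a diary entry, although an ongoing record is promised

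*Protocol*

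**What the plan says.** - Protocol, Session 1: watch and diary are handed out on Monday, "allowing for ongoing record and feedback of their sleep parameters throughout their time in the program".
- Protocol, Summary table of sessions: the columns headed as measurement tools mark diary and actigraphy from Monday onwards. The Tuesday row reads "Nil active intervention for Day 2 participants complete diary +/- nurse", and the same cell goes on to mention Day8 participants. Thursday has no content, only the two marks. The last row is "Friday PM 9 - 9:30pm", also marked for both. No Saturday or Sunday row follows.
- Protocol, Appendices, Sleep Diary: five rows, DAY 1 to DAY 5, with no weekday names. The first column is headed "LAST NIGHT I WENT TO BED AT", so each entry describes the night just ended.
- Protocol, Participant Time Line: the diary is a weekly item.
- Protocol, Administrative Information: self-reported duration is a key secondary outcome with no instrument named. Sleep efficiency is a key secondary outcome with actigraphy given as its source.
- Protocol, Secondary objectives: "Sleep efficiency- percentage time in bed vs percentage time asleep". The source of time in bed is not stated.
- Protocol, Session 2: actigraphy printouts are discussed with participants against their own diaries.

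**The concern.** The form and the table do not deliver the record that the Session 1 text promises. The table is more than a list of sessions. Tuesday (for Day 2 participants) and Thursday have little or no programme content and appear because measurements are taken, so the absence of Saturday and Sunday carries information. A five-row form used once per weekly cycle cannot cover seven nights.

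Three things are at stake:

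- self-reported duration, if it is taken from the diary;
- the Wednesday feedback, which sets diary against actigraphy and is part of the intervention;
- sleep efficiency, but only if someone later uses diary bedtimes to define time in bed. The diary is the only nightly record of going to bed and getting up that the protocol describes.

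Read literally, the table also leaves weekend actigraphy unscheduled.

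**Working it through.** The plan gives no figure of its own to reproduce, so this is a count of nights.

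**Inputs.** Five rows per sheet, each about the previous night (Sleep Diary). One sheet per weekly cycle (an assumption, taken from the weekly entry in the Participant Time Line). Hand-out on Monday at 11:30am (Summary table of sessions). Minimum participation of two weeks (Interventions).

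**Rule.** An entry made on day *d* describes the night from *d* − 1 to *d*.

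**Which day is Day 1?** The Tuesday cell does not settle it. If Monday is Day 1, Tuesdays are Days 2, 9, 16. If Tuesday is Day 8, Tuesdays are Days 1, 8, 15. The labels differ by 8 − 2 = 6, which is not a multiple of 7, so they cannot both hold for one start day.

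**Coverage per week**

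| Reading | Entries | Nights covered | Nights missed | Share |
|---|---|---|---|---|
| A. Day 1 = Monday | Mon–Fri | Sun–Thu | Fri, Sat | 5/7 = 71% |
| B. Day 1 = Tuesday, all rows used | Tue–Sat | Mon–Fri | Sat, Sun | 5/7 = 71% |
| C. Day 1 = Tuesday, entries stop on Friday | Tue–Fri | Mon–Thu | Fri, Sat, Sun | 4/7 = 57% |

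Reading B needs a Saturday entry that the table does not mark. Saturday night is missed in all three, and Friday night in A and C.

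**Nights with both diary and watch, over the 14 nights from the first Monday**

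- A: 4 (Mon–Thu, week 1) + 1 (the Sunday between) + 4 (Mon–Thu, week 2) = 9; 9/14 = 64%. If the participant is still there for the next Monday's entry, 10/14 = 71%. The first row describes the Sunday night before the watch was issued and has no actigraphy to pair with.
- B: 5 + 5 = 10; 10/14 = 71%.
- C: 4 + 4 = 8; 8/14 = 57%.

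**Effect on an estimate (illustration; the deficits are assumptions).** Suppose sleep is *D* minutes shorter on each of two unrecorded nights. The diary's weekly mean is then too high by 2*D*/7: 8.6 min at *D* = 30 and 17.1 min at *D* = 60. The Statistical Analysis Plan section, however, estimates a within-person difference of means. Its error is (2/7) × (*D* at end − *D* at start):

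- deficit of 30 at both ends: (2/7) × 0 = 0;
- deficit growing from 30 to 60: (2/7) × 30 = 8.6 min too favourable;
- deficit shrinking from 60 to 30: 8.6 min too unfavourable.

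**The case against.** The case against is substantial, and much of it stands.

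- *Sleep efficiency.* A reader might infer that it cannot be derived for weekend nights. The documents do not support that. Administrative Information assigns it to actigraphy, and Study Procedure Risks describes a watch that records all the time. No passage says diary times set the time-in-bed interval, and that choice may be made in an analysis plan not shown here.
- *Self-reported duration.* A reader might infer that it rests on weekday nights only. Item 4 of the modified PSQI asks for hours of sleep with the past week as its frame, weekend included. It is, however, a single usual value taken in the first and last weeks, so it cannot replace nightly entries.
- *The booster night.* A reader might infer that Friday night is never diarised. That depends on the unsettled start day, since reading B covers it. The diary mark on the Friday evening row does not decide the matter, because an entry made then could only describe the night before.
- *The watch.* The statement that "you can record continuously for 24 hours per day for days, weeks or longer" describes actigraphy in general, and nothing says the watch comes off on Friday. The missing weekend rows leave wear unscheduled; they do not show that recording stops.
- *Overstated effect.* A reader might take 9 to 17 minutes as bias in the programme's effect. Those figures concern a weekly level; a constant weekend deficit cancels in the planned comparison.
- *Extra sheets* are not excluded, and the table is titled as one of sessions.

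What survives is the mismatch itself. One sheet per cycle falls short by at least two nights, and the table lists session-free weekdays but no weekend day.

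**Conclusion.** The point holds as an inconsistency between the promised ongoing record and the form and table meant to produce it. With one sheet per weekly cycle, at least 2 of 7 nights (29%) have no diary entry. Saturday night is lost on each reading consistent with the Monday hand-out, and Friday night as well if Day 1 is Monday.

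The consequence is limited to diary-based self-reported duration, the diary-actigraphy comparison in the Wednesday feedback, and any time in bed taken from the diary. The primary outcome, actigraphic sleep duration, and actigraphic sleep efficiency are untouched if the watch is worn continuously. They would be affected only if the table's Monday-to-Friday actigraphy marks were followed literally.

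No direction of bias in the within-person change can be claimed. It needs a weekend difference that changes over the stay, and without weekend rows the diary could not show one. The conclusion assumes one sheet per cycle and that no table or form rows were lost in the reading of the PDF.

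**What to change.** 1. Print the diary with seven rows, DAY 1 to DAY 7.
2. Add Saturday and Sunday rows to the Summary table of sessions, marked for both sleep diary and actigraphy.
3. Reconcile the Day 2 and Day8 labels in the Tuesday cell so that the diary's start day is fixed. That cell also refers to intervention content, so which label is right is for the investigators to settle.
4. If the first entry falls on the day of hand-out, label it as the night before the watch was issued and do not pair it with actigraphy.

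A separate display of Friday night, or a nightly efficiency formula built on diary times, is optional and not needed to close the gap.

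The cost is one reprinted form and two table rows, a few more diary prompts for weekend nursing staff, and probably some missing weekend rows.

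### The PSQI and one-item sleep rating are listed after the participant has been shown his actigraphy, and nothing in the protocol requires the rating to come first

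*Protocol*

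**What the plan says.** Under Session 2 of the protocol, watches are collected before the Wednesday session and the research assistant analyses the data. "A visual representation of sleep duration and activity for each patient will be printed prior to the session and given to the registrars". Of the sessions themselves the protocol says: "They are facilitated by two psychiatry registrars". On feedback it says: "During these sessions, printouts will be discussed individually with participants, especially with respect to their self-evaluation in their Sleep Diaries". The same section also places the questionnaire: "Patients in their initial and final weeks of the program will be asked to complete the Pittsburgh Sleep Quality Index".

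The Summary table of sessions puts all of this in one half-hour slot. Its last two entries are "Present sleep results • Administer PSQI and one-item Sleep Quality measure (start and terminating session only".

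The modified PSQI in the appendices covers the past week. Item 4 asks "How many hours of actual sleep do you get at night", and item 9 asks for a rating of overall sleep quality. In Administrative Information, the key secondary outcomes include sleep quality (weekly VAS, and PSQI at start and end) and, as a separate entry, "Self-report duration". PSQI improvement is also the first secondary objective and one of the hypotheses. The Statistical Analysis Plan section of the protocol estimates effects by within-person differences of means.

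**The concern.** A self-report measure adds to actigraphy only if the participant answers from his own experience of sleep. If he has just been shown his recorded sleep duration and talked it through against his diary, his answer on hours slept can move toward the displayed value, and his quality rating can move with the tone of the discussion. The ratings are also placed in a session run by the clinicians who deliver the sleep education. The protocol tells participants completing the satisfaction survey that practitioners will not see their answers. It gives no matching assurance for the PSQI or the one-item rating.

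At stake is how a change in PSQI score is read. Some of it could come from the measurement procedure and not from sleep, and there is no randomised comparator to absorb that part. The protocol's own Actigraphy background warns that the subjective nature of questionnaires can be a problem for detecting change in small pilot studies.

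**Working it through.** The protocol states no figure on this point, so there is nothing to reproduce. The check compares the sections on order and then counts nights.

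**Order of feedback and rating**

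- Summary table, Wednesday slot: outdoor session, psychoeducation, presentation of results, then PSQI and one-item rating.
- Session 2 prose: printout discussion, then group psychoeducation, then PSQI.
- The two disagree on whether psychoeducation or feedback comes first, so at least one is not a strict running order. Both put the PSQI last.
- Participant Time Line: self-report measures at recruitment, weekly and at discharge. A PSQI truly given at recruitment would precede any printout, but Session 2 places the PSQI on Wednesday. The two places do not agree.
- No section says that the forms are completed before the printout is shown, or that someone other than the facilitators collects them.

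**Which items are exposed**

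- The printout shows sleep duration, and PSQI item 4 asks for sleep duration.
- PSQI item 9 and the one-item measure ask for sleep quality, which the discussion bears on directly.
- Diary entries are made day by day outside the session. They are exposed through feedback on earlier Wednesdays, and on the day itself only if an entry is revised after the discussion.

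**Nights in the PSQI window that a printout can show**

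Inputs: watch issued at the Monday session (Session 1); printout on Wednesday (Session 2); recall window of one week, that is 7 nights (PSQI appendix); minimum participation of 2 weeks (Interventions).

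- First Wednesday: the nights of Monday and Tuesday, so at most 2 of 7. 2/7 = 29%.
- Final Wednesday: counting the issuing Monday as day 1, Wednesdays fall on days 3 and 10 of a 14-day stay. By day 10 the watch has been available for 9 nights, so up to 7 of 7 nights in the window are covered (100%). At least one feedback session (day 3) has already taken place.

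**Consequence for the within-person difference**

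Suppose a participant misjudges his sleep by d minutes, and feedback moves his answer toward the printout by a share s1 at the first rating and s2 at the last. With no change in sleep, the reported change is (s2 − s1) × d. This is zero if s1 = s2. The unequal coverage and the earlier feedback give no reason to expect s1 = s2, but the documents supply neither share nor d, so neither sign nor size can be computed.

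**The case against.** The strongest reply is that the bullets describe content and not a timetable, and that the prose orders other items differently. That stands: the order is inferred, not stated. It does not remove the point, because both places list the rating last and nothing in the protocol asks for the safer order.

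Feedback is also a deliberate part of the intervention; Interventions lists ongoing sleep quality monitoring and feedback. This stands as well. Changing the order takes away only the same-day influence, and what participants learned in earlier weeks properly remains.

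A reader might infer more than the documents support in four respects:

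- That self-report outcomes **are** contaminated by some number of minutes. Both ratings are listed after a printout, so only the difference in influence matters. It may be zero, and any figure in minutes would rest on invented inputs.
- That the registrars are the participants' treating doctors, or that they hand out the PSQI. The protocol says only that they run the session. The Physical Data section describes the forms as completed by the patient and marked only with the Participant ID.
- That self-report duration as an outcome is directly affected. No instrument is named for it. If it is taken from the diary, the same-day effect largely disappears.
- That the weekly VAS is taken after feedback. Its timing within the week is not given.

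Finally, this is an open-label pilot with a largely descriptive analysis, and the primary outcome comes from the watch. That limits the importance of the point, but testing the methodology is one of the pilot's stated aims.

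**Conclusion.** The point holds as an avoidable weakness in the secondary self-report outcomes. Followed as listed, the plan leaves PSQI items 4 and 9 and the one-item rating open to same-session anchoring on the printout and to influence from the session's facilitators. Exposure is unequal, at most 2 of 7 nights against up to 7 of 7, so the effect need not cancel in the planned difference. Direction and size are unknown. The order of rating does not affect actigraphic sleep duration.

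The conclusion assumes that the listed order is the order followed, that the PSQI is given on Wednesday as Session 2 says, and, for the count of 7, that the watch is worn every night and the printout spans the week. It is worth correcting before enrolment, but it does not threaten the pilot's primary result.

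**What to change.** Reorder Session 2, in both the prose and the summary table:

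- The PSQI and the one-item rating are completed and collected by the research assistant in the existing Wednesday pre-session, before any printout is shown.
- Diary entries already made are not revised after the discussion.

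Reconcile this with two other places:

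- the Participant Time Line, which has self-report at recruitment, weekly and at discharge;
- the outcome list, which makes the VAS weekly, whereas the session table limits its one-item measure to the first and last sessions. State whether these are the same item and, if not, when the VAS is taken.

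It would also help to name the instrument that supplies self-reported duration.

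The cost is a few lines of text: same forms, same day, existing staff, and no feedback withheld. Same-day influence is removed; the influence of earlier weeks is not, and the report should say so.
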